7.7.7 Procedure of Reporting Serious Adverse Events

The Sponsor-Investigator(s) primary responsibilities for safety reporting are to identify and follow-up on Serious Adverse Events (SAEs) experienced by participants in the study and to forward the information to the local regulatory authorities and Merck, as required by local regulations (for regulatory reporting) and as required by the ISS agreement (for reporting to Merck).

The following reportable events must be submitted to Merck within 2 business days or 3 calendar days (whichever comes first) using the applicable safety report form provided. The Principal Investigator(s) will assume responsibility for submitting the reportable event(s) to Merck as well as ensuring that any local reporting requirements are completed in parallel.

- Serious Adverse Events (see section 7.4.2)
- Exposure during Pregnancy or Breastfeeding (even if not associated with an adverse event)
- Occupational exposure (even if not associated with an adverse event)
- Potential drug-induced liver injury (Hy's Law cases): These events are considered important medical events and should be reported as SAEs.

Contact information for submission of reportable events to Merck:

[contact] or

E-mail: [contact]

Specifying:

- PROTOCOL Number and/or Title
- Funder's Study Identifier
- SUBJECT Number
- Principal Investigator Name
- Sponsor Name
- SAE/ONSET DATE

7.7.8 Monitoring of subjects with Adverse Events

Any AE that occurs in the course of a clinical study must be monitored and followed up until the last study visit. It is the responsibility of the Investigator(s) that any necessary additional therapeutic measures and follow-up procedures are performed.

8. STATISTICS

8.1 Statistical Analysis

- Patients who complete TACE will be considered as the study population for primary and secondary endpoints.
- The primary endpoint - the rate of patients amendable to curative surgical intervention will be estimated based on exact binomial distribution.

- Objective response rate (ORR), pathological response rate, and number of patients amendable to curative interventions and / or radiological CR will be expressed based on exact binomial distribution.
- Survival outcomes, including TTP, PFS and OS and their corresponding 95% confidence interval, will be estimated using Kaplan-Meier method.
- Patient reported QoL scores will be estimated at baseline, during and following therapy. Scores at each time point will be summarized with descriptive statistics including means, standard deviations, median and range. The changes from baseline during therapy and after therapy will be calculated for each patient and also summarized with means and standard deviations/95% CI. Linear mixed-effect model will be used to study the longitudinal changes of QoL scores.
- All of the tests and reported P values will be 2-tailed, and P<0.05 will be considered statistically significant. The analyses will be performed using statistical software packages SPSS and R.

Procedures for Handling Missing, Unused, and Spurious Data: All available data will be included in the data listings and tabulations. Where appropriate, imputations of values for missing data for primary and secondary efficacy analyses will be performed as specified in the Statistical Analysis Plan. All data recorded on the CRF will be included in the data listings that will accompany the clinical study report.

If, after the study has begun, but prior to the conduct of any analysis, changes made to primary and / or key secondary endpoints, or the statistical methods related to those hypotheses, then the protocol will be amended. Changes to exploratory analyses made after the protocol finalized will be documented and referenced in the final report. Post hoc exploratory analyses will also be identified in the final report.

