2.2 Secondary Objectives

1. To assess the number of patients amenable to curative surgical interventions and/or achieve radiological complete response in HCC patients treated with combined TACE and SBRT followed by Avelumab
2. To assess the objective response rate in HCC patients per mRECIST treated with combined TACE and SBRT followed by Avelumab
3. To evaluate the time-to-progression (TTP), progression-free survival (PFS) and overall survival (OS) in HCC patients treated with combined TACE and SBRT followed by Avelumab
4. To measure the toxicities in HCC patients treated with combined TACE and SBRT followed by Avelumab
5. To evaluate the patient-reported quality of life (QoL) treated with combined TACE and SBRT followed by Avelumab
6. To describe the pathological response among HCC patients amenable to surgery after receiving combined TACE and SBRT followed by Avelumab
7. To assess the disease control rate (DCR) in HCC patients treated with combined TACE and SBRT followed by Avelumab
8. To assess the local control rate among HCC patients treated with combined TACE and SBRT followed by Avelumab
9. To evaluate the duration of response among HCC patients responded to combined TACE and SBRT followed by Avelumab
10. To describe the pattern of failure at the time of progression

11. To assess the objective response rate in HCC patients per RECIST 1.1 treated with combined TACE and SBRT followed by Avelumab
12. Collection of bio-specimens for future correlative studies in patients treated with TACE and SBRT followed by Avelumab

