7.3.2 Secondary Endpoints

- Response rate measured by mRECIST criteria:

Complete response (CR): Disappearance of any intra-tumoral arterial enhancement in all target lesions

Partial response (PR): At least a 30% decrease in the sum of diameters of viable (enhancement in the arterial phase) target lesions, taking as reference the baseline sum of the diameters of target lesions

Stable disease (SD): Any cases that do not qualify for either partial response or progressive disease

Progressive disease (PD): An increase of at least 20% in the sum of the diameters of viable (enhancing) target lesions, taking as reference the smallest sum of the diameters of viable (enhancing) target lesions recorded since treatment started

- Number of patients amenable to curative surgical interventions and/or achieve radiological complete response: defined as number of patients receiving curative surgical intervention or transplantation after successful downstaging (i.e. equivalent to primary endpoint) plus number of patients achieving radiological CR per mRECIST criteria. This endpoint is to reflect the number of patients achieve complete tumor clearance and potentially cure.
- Time to progression (TTP): measured from the date of first study treatment to radiographically documented progression according to mRECIST 1.1. This does not include death from any cause.
- Progression-free survival (PFS): measured from the date of first study treatment to radiographically documented progression according to mRECIST 1.1 or death from any cause (whichever occurs first). Participants alive and without disease progression or lost to follow-up will be censored at the date of their last radiographic assessment.
- Overall survival (OS): measured from date of first study treatment to the date of death from any cause. Participants alive or lost to follow-up will be censored at the date of their last visit.
- Quality of life (QoL): as assessed by the European Organization for Research and Treatment of Cancer Core Quality of Life Questionnaire (EORTC-QLQ-C30) and the Functional Assessment of Cancer Therapy–Hepatobiliary (FACT-Hep) questionnaires
- Safety outcome measures: Incidence, nature, and severity of adverse events graded according to the United States National Cancer Institute The Common Terminology Criteria for Adverse Events (NCI CTCAE 4.0)

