8.2 Sample Size Calculation

H0: The null hypotheses of no difference in the number of patients who can undergo surgery: similar to the historical result of QMH, 5% of patients can undergo surgical intervention after TACE.

H1: The alternative hypotheses of treatment efficacy: the experimental treatment would result in 20% of study population who can undergo surgical resection after treatment response.

To detect 15% of differences from 5% to 20% in the number of patients proceeding to surgery, with Type I error of 0.05 and 80% power, assume 10% patients who have withdrawn may withdraw consent and patients who cannot be contacted during survival follow-up period, withdrawn subjects are only to before starting their protocol treatment. Patients will not be replaced once their protocol treatment started. The target accrual is 33 patients. Simon's two-stage optimal design will be used. In the first stage ten patients will be enrolled. If at least one is amenable to curative surgical intervention, the study can proceed to the second stage and an

additional 19 patients could be recruited. If at least 4 of the total 29 patients **are amenable to curative surgical intervention**, the treatment will be considered worthy of further investigation.

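### Section 8.1 limits every primary and secondary endpoint to patients who complete TACE, so a patient who starts but does not complete it is treated, not replaced and not analysed

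*Protocol*

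**What the plan says.** - **Population (8.1):** "Patients who complete TACE will be considered as the study population for primary and secondary endpoints". The protocol does not define what completing TACE means.
- **Sequence (6.3, 6.4, 6.5):** TACE comes first, SBRT follows 21 to 35 days later, and avelumab follows SBRT.
- **Replacement (8.2):** "Patients will not be replaced once their protocol treatment started". The 10% allowance covers withdrawals before protocol treatment only.
- **Time origin (7.3.2):** OS is "measured from date of first study treatment to the date of death from any cause". TTP and PFS start at the same point.
- **Safety is a secondary endpoint (7.3.2):** "Safety outcome measures: Incidence, nature, and severity of adverse events". The matching objective in 2.2 is "To measure the toxicities in HCC patients treated with combined TACE and SBRT followed by Avelumab".
- **Not restricted to completers:** 7.7.6 has all adverse events entered in the CRF, with causality to TACE assessed. Section 8.1 itself puts all available data into listings and tabulations. The stopping rule in 8.3 counts enrolled or recruited patients.
- **Null rate (8.2):** historically, "5% of patients can undergo surgical intervention after TACE".

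**The concern.** Completing the first treatment step is an outcome of treatment, not a baseline characteristic. Someone whose TACE is abandoned has been exposed, has a running survival clock and cannot be replaced, yet does not count. Such patients are unlikely to reach curative surgery, and some may have stopped because of toxicity, so leaving them out should flatter the results.

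Sections 8.1, 8.2 and 8.3 also rest on three different bases: TACE completed, treatment started, and patient enrolled. Because completion is undefined, someone must decide case by case, in an open single-arm trial, whether a partly performed procedure puts a patient in the analysis. At stake are the conversion rate that drives the go/no-go decision, the survival curves and the reported toxicity rate.

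**Working it through.** **1. The plan's own design.** Inputs from 8.2: null rate 0.05, alternative 0.20; continue if at least 1 of 10 converts; success if at least 4 of 29 convert. With X1 ~ Bin(10, p) and X2 ~ Bin(19, p),

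P(success) = Σ P(X1 = x) · P(X2 ≥ 4 − x), summed over x ≥ 1.

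At p = 0.05 the terms for x = 1, 2, 3 and x ≥ 4 are 0.02097 + 0.01831 + 0.00652 + 0.00103 = **0.0468**. At p = 0.20 the sum is **0.801**. The chance of stopping after stage 1 under the null is 0.95^10 = 0.599. Accrual is 29/0.9 = 32.2, rounded up to 33. The stated design reproduces.

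**2. Who is excluded.**

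| Patient | In the 8.1 population? |
|---|---|
| Withdraws before TACE | No (the case covered by the 10% in 8.2) |
| Starts TACE, does not complete it | **No**, although treated, not replaced and on the survival clock |
| Completes TACE, then progresses, dies, or never receives SBRT or avelumab | Yes, as a non-conversion |
| Completes TACE and is operated on | Yes, as a conversion |

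Only the second row is a problem.

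**3. Effect on the estimated rate.** With 4 conversions among 29 completers the rate is 4/29 = 13.8%. If one or two further patients started TACE without completing it, the rate among all who started is 4/30 = 13.3% or 4/31 = 12.9%. The counts of non-completers are illustrative.

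**4. Effect on the type I error.** Let f be the share of treated patients who do not complete TACE (assumed range 0% to 10%). Assume that:
- the true null rate is 5% of all treated patients;
- no non-completer converts;
- the 10 and 29 in the rule are completers.

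The rate among completers is then 0.05/(1 − f), which goes into the formula in step 1. About 29/(1 − f) patients must start TACE.

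| f | Null rate among completers | Type I error | Starters needed |
|---|---|---|---|
| 0% | 0.0500 | 0.0468 | 29.0 |
| 2% | 0.0510 | 0.0498 | 29.6 |
| 3% | 0.0515 | 0.0513 | 29.9 |
| 5% | 0.0526 | 0.0546 | 30.5 |
| 10% | 0.0556 | 0.0641 | 32.2 |

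The error passes 0.05 between f = 2% and 3%. All rows fit within the accrual of 33.

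**5. When the inflation does not arise.** If the historical 5% was measured among patients who completed TACE, the null among completers is 5% by definition and the error stays at 0.0468. If the 10 and 29 are patients who started TACE, the success threshold is a count of conversions that non-completers do not alter, so only the denominator of the reported rate moves.

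**The case against.** The strongest reply is that the set is nearly all treated patients. TACE is described as a single procedure, so non-completion means an abandoned procedure. Section 6.3.1 places angiography first, partly to rule out main portal vein occlusion, which is itself an exclusion. Some abandoned cases would be ineligible patients rather than treatment failures. The benchmark is worded as surgery after TACE, so the populations may already match. A separate safety set may also be defined in the SAP, which is not at hand. This all limits the size of the effect. It does not remove the conflict, because the protocol states a population for every endpoint rather than leaving one open.

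Four stronger readings are tempting, and the documents do not support them:

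- *All early failures are removed.* Only failures to complete TACE are. Later decompensation, progression or death stays in the denominator.
- *The primary endpoint loses numerator and denominator alike.* A patient with abandoned TACE would rarely reach surgery after down-sizing, so the loss is from the denominator.
- *Those patients' adverse events disappear.* Recording (7.7.6), listings (8.1) and toxicity stopping (8.3) still cover them. Only the formal safety endpoint, read literally, does not.
- *Pathological response would be divided by all TACE completers.* The objective is "To describe the pathological response among HCC patients amenable to surgery after receiving combined TACE and SBRT followed by Avelumab", and the definition in 7.3.2 needs a surgical specimen. The general sentence in 8.1 does not override that. Duration of response is likewise already confined to responders.

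**Conclusion.** The point holds in a limited form. The 8.1 population is selected after treatment starts and does not fit the no-replacement rule in 8.2, the time origin in 7.3.2 or the enrolled base in 8.3.

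For the conversion rate the bias is favourable, provided non-completers do not reach surgery. For survival and safety the same direction is expected if non-completion goes with a worse course, which is plausible but not documented. The size is small: about half a percentage point on the conversion rate for each non-completer in the example. The type I error would be 0.0513 to 0.0641 for non-completion of 3% to 10%, against 0.0468 as designed.

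Those error rates are conditional. The protocol gives no non-completion share, does not say whether the 5% covers all treated patients, and does not say whether 10 and 29 count completers or starters. The case for changing the sentence rests on the treated-but-unanalysed patient, which does not depend on any of these.

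**What to change.** Replace the population sentence in 8.1 with: *All patients who start TACE form the population for the primary and secondary efficacy endpoints and for safety; patients who do not undergo curative surgery, including those who do not complete TACE, count as failures for the primary endpoint.* Define the start and the completion of TACE for analysis purposes, keep completers as a sensitivity set, and state in 8.2 that 10 and 29 are patients who started TACE.

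The 0/10 and 4/29 rule and the accrual of 33 stay as they are. The cost is slightly less favourable rates. There is also some loss of power if the 20% alternative was meant for completers only. The rate among all starters is then 0.20 × (1 − f), and power falls from 0.801 to 0.782 at f = 3%, 0.768 at 5% and 0.730 at 10%. If 20% was meant for all treated patients, power is unchanged.

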6.3.3 TACE Toxicity Assessment During Therapy

Patient should be seen at least once after TACE before initiation of SBRT. SBRT can be commenced if there is no grade 3 or 4 toxicity, bilirubin ≤ 3.0 mg/dL, Child Pugh score ≤ 7 and the treating physician recommends continuation. Otherwise, a delay in SBRT should occur until toxicities resolve.

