6.4.5 Radiotherapy Toxicity Assessment During Therapy

Patients will be assessed at least once during radiation therapy for toxicity. Radiation therapy will continue as planned as long as there is no grade 3 or 4 toxicity, bilirubin ≤ 3.0 mg/dL, Child Pugh score ≤ 7 and the treating physician recommends continuation. Otherwise, a delay in radiation therapy should occur with possible continuation of radiation after toxicities resolve. If the patient discontinues radiation therapy prematurely, the patient may be considered for study Avelumab, if the Child score is Child Pugh ≤ 7 and the treating physician recommends protocol treatment continuation.

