6.5 Checkpoint Inhibitor: Avelumab

Avelumab will be started 14 days (or 14-18 days) upon completion of SBRT.

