7.7.6 Methods of Recording Adverse Events

All AEs must be documented in the appropriate section of the CRF. An SAE report form (initial or follow up) must be completed in addition.

The following aspects must be recorded for each event in the CRF:

A description of the AE in medical terms, not as reported by the subject;

- The date of onset (start date)
- The time of onset (start time)
- The date of recovery (stop date)
- The time of recovery (stop time)
- The severity of the sign and/or symptom or clinically significant abnormal laboratory value according to NCI-CTC, Version 4.0. If no toxicity grade is described for a given sign, symptom or abnormal laboratory value, the Investigator(s) will grade the severity as mid (grade 1), moderate (grade 2), severe (grade 3), or life-threatening or disabling (grade 4).

- Death (grade 5) as defined by NCI-CTCAE v.4.0 is mainly regarded as an outcome and will be documented accordingly (see below).
- The causal relationship to Avelumab, TACE and radiotherapy as assessed by the Investigator(s); the decisive factor in the documentation is the temporal relation between the AE and the study drug. The following judgments of the causality to study drug or study procedures are to be used:
 - Not Related = not suspected to be reasonably related to the investigational product. AE could not medically (pharmacologically/ clinically) be attributed to the investigational product under study in this protocol
 - Related = suspected to be reasonably related to the investigational product. AE could medically (pharmacologically/ clinically) be attributed to the investigational product under study in this protocol
- Action taken on Avelumab (none, medication discontinued, dose reduction, medication delayed, reduction of infusion rate).
- Other action (none, concomitant medication given, new or prolonged hospitalization, procedural surgery).
- The outcome according to the following definitions:
 - Recovered without sequelae (AE disappeared)
 - Recovered with sequelae (AE has resulted in permanent disability/incapacity)
 - Not yet recovered
 - Not recovered at death
 - Change in toxicity grade/severity or seriousness (e.g., an AE with no change of toxicity grade but newly classified as an SAE due to hospitalization)
 - Fatal (AE resulted in death)
- Concomitant medication given: Yes or No (Note: If this question is answered “Yes” the corresponding serious criteria must be ticked)
 - Subject died
 - Life-threatening

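### Section 8.1 makes TACE completers the population for adverse events too, so avelumab-specific rates are diluted if any completer never starts avelumab

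*Protocol*

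**What the plan says.** All references are to the protocol.

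- **Population.** Section 8.1 states: "Patients who complete TACE will be considered as the study population for primary and secondary endpoints". It makes no exception for safety, and no safety or avelumab-treated set is defined elsewhere.
- **Safety is a secondary endpoint.** Section 7.3.2 includes "Safety outcome measures: Incidence, nature, and severity of adverse events". The matching objective in section 2.2 is "To measure the toxicities in HCC patients treated with combined TACE and SBRT followed by Avelumab".
- **Avelumab comes last.** Section 6.4 places SBRT 21 to 35 days after TACE. Section 6.5 then says "Avelumab will be started 14 days (or 14-18 days) upon completion of SBRT".
- **There are exits in between.** Section 6.3.3 says "SBRT can be commenced if there is no grade 3 or 4 toxicity" and adds bilirubin, Child-Pugh and physician conditions; otherwise SBRT is delayed. Section 6.4.6 ends radiation for grade 4 gastrointestinal or other non-hematological toxicity. After an early SBRT stop, section 6.4.5 says only that "the patient may be considered for study Avelumab, if the Child score is Child Pugh" 7 or lower and the physician agrees. Section 7.5 removes patients for progression, unacceptable toxicity or withdrawal. Section 8.2 does not replace patients once treatment has started.
- **Avelumab-specific events are singled out.** Section 7.7.3 names infusion-related and immune-mediated reactions as events of special interest for avelumab. Section 7.7.6 records causality separately for avelumab, TACE and radiotherapy, and section 6.6 records treatment details for all three.

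**The concern.** A patient who completes TACE but never receives avelumab cannot have an avelumab infusion reaction or an avelumab immune-related event. Under section 8.1 that patient still counts in the denominator. The resulting error runs one way: it lowers the apparent rate of reactions to the only investigational product in the trial (section 6.1). Several of the exits are triggered by toxicity or poor liver function, so poor tolerance of the earlier steps could make avelumab look safer.

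The same sentence has a second effect. Someone who starts TACE but does not complete it has been treated, yet falls outside the population, and any toxicity that person had is lost from the safety endpoint.

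At stake is the safety description that readers will take from the trial: how often avelumab causes its characteristic reactions in patients who get it after TACE and SBRT, and how toxic the regimen is in everyone who begins it.

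**Working it through.** **1. The protocol's own figures.** Section 8.2 gives a Simon optimal design for 5% against 20%, with 10 patients in stage one, 29 in total and at least 4 successes needed. An exact calculation gives type I error 0.0468 and power 0.801, and a search over designs returns this one as optimal. Inflating for 10% withdrawal: 29 / (1 − 0.10) = 32.2, rounded up to 33, as stated. The section 8.3 lower bounds also reproduce: 5/8 gives 34.46%, 8/16 gives 31.78%, 11/24 gives 31.48% and 14/33 gives 30.5%. No stated figure is wrong; the question is only the denominator rule. The numbers 29 and 33 serve below as plausible counts of TACE completers.

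**2. Formula.** Let N be the number who complete TACE, k the number of those who never receive avelumab, and p the incidence of an avelumab-specific reaction among those who do receive it.

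Reported incidence = p × (N − k) / N

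The relative understatement is k / N, which is zero only when k = 0.

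**3. Assumptions.** The protocol gives neither k nor p. The 10% allowance in section 8.2 appears to concern withdrawal before treatment starts, so it does not supply k. The values below are illustrative. Of the rates, 30% is the level section 8.3 calls unacceptable for its own set of events; 20% and 45% are added to show the spread.

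**4. Results for N = 29.**

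| Never given avelumab (k) | (N − k)/N | True 20% | True 30% | True 45% |
|---|---|---|---|---|
| 0 | 29/29 = 1.000 | 20.0% | 30.0% | 45.0% |
| 1 | 28/29 = 0.966 | 19.3% | 29.0% | 43.4% |
| 3 | 26/29 = 0.897 | 17.9% | 26.9% | 40.3% |
| 6 | 23/29 = 0.793 | 15.9% | 23.8% | 35.7% |
| 9 | 20/29 = 0.690 | 13.8% | 20.7% | 31.0% |

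For N = 33 and a true 30%, the reported rate is 29.1%, 27.3%, 25.5%, 23.6% or 20.9% when 1, 3, 5, 7 or 10 patients miss avelumab.

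**5. One worked case.** Suppose 6 patients have an avelumab reaction and 23 of 29 TACE completers received the drug. Over exposed patients this is 6/23 = 26.1% (exact 95% CI 10.2% to 48.4%). Over TACE completers it is 6/29 = 20.7% (8.0% to 39.7%). The shift of 5.4 percentage points is small against the sampling error, but it is systematic and avoidable.

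**6. Do the decision rules use this rate?** The go criterion in section 8.2 counts patients amenable to surgery. The stopping rule in section 8.3 counts patients with events against patients enrolled. Neither divides avelumab reactions by TACE completers.

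**The case against.** **The protocol never says that avelumab events will be divided by TACE completers.** Its safety endpoint is overall adverse-event incidence, its objective concerns the whole sequence, and the causality field in section 7.7.6 is a recording rule. For the toxicity of the whole strategy, keeping patients who stopped early is defensible; restricting to avelumab recipients conditions on having come through TACE and SBRT. This stands for whole-regimen toxicity. A reader might infer that TACE completers are the wrong group for every safety table, and the protocol does not support that. What remains is that section 8.1 offers no other denominator for the avelumab events that section 7.7.3 singles out.

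**Adverse-event tables are usually left to the SAP.** True of their layout, and section 8.1 has no bullet on adverse-event methods. But the population is stated outright, for all secondary endpoints, and section 8.1 defers to the SAP only on imputation. A SAP could add exposed-patient tables, but replacing the safety denominator would depart from the protocol's stated rule.

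**The size is assumed.** It is. Much of the cited text describes delay until recovery rather than exit, and a patient who stops SBRT early may still receive avelumab. A reader might infer that avelumab incidence will certainly be understated. The protocol supports only the conditional statement: it is understated if at least one completer never starts.

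**It changes no decision.** This stands. A reader might infer that the dilution biases the choice to continue or stop. As step 6 of the working shows, neither rule uses this rate.

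**Conclusion.** The point holds in a limited form. Section 8.1 fixes TACE completers for all secondary endpoints, section 7.3.2 makes adverse-event incidence one of them, and the protocol itself provides routes by which a TACE completer never receives avelumab. Read literally, rates of avelumab-specific reactions are diluted by the share of completers who were never exposed.

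The size rests on a number the protocol does not give. For 1 to 9 of 29 unexposed, the relative understatement is 1/29 = 3.4% to 9/29 = 31.0%, so that a true 30% reads as about 29% to 21%. If everyone starts avelumab, there is none.

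Independently of that, treated patients who do not complete TACE are left out of the safety population. The protocol gives no figure for them, and the effect on the overall rate could go either way, depending on whether they had events.

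Both effects are confined to descriptive safety reporting. The primary endpoint, the two-stage design, the go criterion and the stopping rule are untouched. The change is still worth making, because the rule is explicit, the avelumab error can run only towards apparent safety, and the remedy is nearly free.

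**What to change.** Amend section 8.1 as follows:

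- Limit the TACE-completer population to the efficacy endpoints, and say explicitly which population applies to quality of life.
- Report overall adverse events for the regimen over all patients who started any study treatment, including those who did not complete TACE.
- Report avelumab-attributed adverse events and events of special interest over patients given at least one avelumab dose.
- Report SBRT-attributed adverse events over patients given at least one fraction.
- Show the number in each denominator, so that a reader can see how many patients stopped between steps.

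No new data are needed: section 6.6 already records treatment details for each component, and section 7.7.6 already records attribution by component. The cost is a short amendment, a few extra table columns, and smaller denominators with wider intervals for the component-specific rates. Those rates describe patients who got as far as that component, so they should be shown beside the overall regimen rate and not in place of it.

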- Pathological response: assessed as the percentage of surface with non-viable cancer cells (represented by necrosis or fibrosis, the ultimate stage of necrosis) in relation to the total tumor area and will be equal to: 100% – viable cancer cells (%). If there are

multiple tumors, the mean percentage will be used. Pathological complete response (pCR) is defined by the absence of viable tumor cells in any nodule.

- Disease control rate: Percentage of patients that had a CR, PR, or stable disease (SD) \geq 6 months per mRECIST
- Local control: defined as absence of recurrence within the high-dose region (80% isodose volume), demonstrated by new enhancement or mRECIST progressive disease
- Duration of response: time from first documented evidence of CR or PR until the first documented sign of disease progression (PD) or death from any cause
- Pattern of failure:
 - (1) In-field failure: defined as recurrence within the high-dose region (80% iso-dose volume), demonstrated by new enhancement or mRECIST progressive disease.
 - (2) Out-field (intra-hepatic): defined as new or mRECIST progressive disease within liver parenchyma, but outside the SBRT treated volume
 - (3) New vascular invasion: defined as new portal or hepatic vein invasion
 - (4) Distant failure: defined as new disease outside liver parenchyma
- Radiological response per RECIST 1.1

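### Section 8.1 gives a pathological response rate an exact binomial over all TACE completers, although the endpoint exists only in operated patients and only pCR is binary

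*Protocol*

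**What the plan says.** **Objective (Protocol 2.2, item 6).** The aim is descriptive and limited to a subgroup: "To describe the pathological response among HCC patients amenable to surgery after receiving combined TACE and SBRT followed by Avelumab". Section 7.3.1 equates being amenable with actually receiving resection or transplantation, so the subgroup is the operated patients.

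**Definition (Protocol 7.3.2).** The endpoint is a percentage: "Pathological response: assessed as the percentage of surface with non-viable cancer cells", taken "in relation to the total tumor area and will be equal to: 100% – viable cancer cells". No cut-off separates responders from non-responders. For a patient with "multiple tumors, the mean percentage will be used". The same bullet then gives one binary outcome: "Pathological complete response (pCR) is defined by the absence of viable tumor cells in any nodule".

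**Analysis (Protocol 8.1).** The first bullet sets the population without exception: "Patients who complete TACE will be considered as the study population for primary and secondary endpoints". The third bullet takes "Objective response rate (ORR), pathological response rate, and number of patients amendable to curative interventions", with or without radiological CR, as one group that "will be expressed based on exact binomial distribution". The bullet does not mention pCR or a subset of operated patients.

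**The concern.** Two printed rules do not fit the endpoint they govern.

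- **Denominator.** The objective concerns operated patients, while the analysis population is everyone who completed TACE. Patients without surgery have no specimen and therefore no value. Dividing by all TACE completers mixes two questions: how many reached surgery, and how well the tumour responded in those who did.
- **Numerator.** A binomial interval needs a yes/no outcome. The endpoint as defined is a percentage, and the term used in 8.1 is not defined anywhere. pCR would serve, but 8.1 does not say that pCR is meant.

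At stake is how the pathological result reads. The same specimens could give a rate several times smaller or larger depending on which section is followed. With so few specimens, a responder cut-off chosen after seeing them could also decide the result.

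**Working it through.** **Step 1. The plan's own figures.** No figure is printed for pathological response, so the check starts from the design in 8.2: 10 patients, then 29 in total; continue with at least 1 success; positive with at least 4; 5% against 20%.

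P(positive | p) = Σ over x = 1 to 10 of b(x; 10, p) × P(Y ≥ 4 − x), with Y ~ Bin(19, p).

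- p = 0.05: 0.0468 (stated type I error 0.05).
- p = 0.20: 0.801 (stated power 80%).
- Accrual: 29/0.9 = 32.2, rounded up to 33.

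The design reproduces, so 29 is a fair denominator for illustration.

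**Step 2. The ceiling.** Let N be TACE completers, R operated patients and C patients with pCR. Then

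C/N = (R/N) × (C/R), and C ≤ R, so C/N ≤ R/N.

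R/N is the primary endpoint rate. At the success boundary it is 4/29 = 13.8%. Under the alternative, 20% of 29 is 5.8, about 6 patients, and 6/29 = 20.7%. Even if all 6 had pCR, the literal rate would be 20.7%, while the rate among operated patients would be 100%.

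**Step 3. Size on assumed counts.** The Protocol gives no expected number of pCRs. I assume half of the operated patients and vary R. The intervals are Clopper–Pearson 95%: lower = Beta(0.025; x, n − x + 1), upper = Beta(0.975; x + 1, n − x).

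| Operated (R) of 29 | pCR (C) | C/29, all TACE completers | C/R, operated |
|---|---|---|---|
| 4 | 2 | 6.9% (0.9–22.8%) | 50% (6.8–93.2%) |
| 6 | 3 | 10.3% (2.2–27.4%) | 50% (11.8–88.2%) |
| 10 | 5 | 17.2% (5.9–35.8%) | 50% (18.7–81.3%) |

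For R = 6 the decomposition is 6/29 × 3/6 = 0.207 × 0.5 = 0.103. With N = 33 instead of 29, the literal rate is 3/33 = 9.1% (1.9–24.3%).

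The pathological result is the same in all three rows. Only the number operated changes, and the literal rate follows it from 6.9% to 17.2%. Its interval is also narrower than the one for operated patients, because unoperated patients add to n although they have no specimen.

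**Step 4. Method against definition.** Of the two quantities in the 7.3.2 bullet, the percentage of non-viable tumour has no cut-off and cannot be a binomial count. pCR can. The exact binomial in 8.1 is therefore valid only if its undefined rate means the pCR rate.

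**The case against.** The best reply is that 8.1 names an overall analysis set and does not say that each endpoint is divided by its size. Objective 6 then picks the operated patients within that set. Duration of response works in the same way: it is defined only for responders, and nobody would add non-responders because of the first bullet of 8.1. If the rate is read as the pCR rate, the exact binomial is correct. The objective is also only descriptive, and 8.1 leaves missing-data handling to the statistical analysis plan.

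Much of this stands. It is a sensible reading, and it rules out two stronger claims that a reader might make. One is that the endpoint has no valid numerator; pCR is one. The other is that unoperated patients are certain to be counted as non-responders; no such rule is printed. A rate over all TACE completers is also a legitimate quantity if labelled as such. What does not stand is that 8.1 says any of this. It states one population for all secondary endpoints, makes no exception, and uses a term defined nowhere.

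A reader might also infer that averaging over nodules distorts the percentage and that area weighting is required, because 7.3.2 refers to total tumour area. The documents do not support that. Section 7.3.2 expressly prescribes the mean for several tumours, so area weighting is a preference. A plain mean favours no nodule, and it agrees with the area-weighted value when nodules are equal in size. Any gap depends on sizes and necrosis values that the Protocol does not give. The choice cannot affect pCR.

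**Conclusion.** The point holds as a conflict between printed rules, and it is minor. Section 8.1 taken literally gives a pathological response rate that is capped by the resection rate (about 20% under the alternative) and does not answer Objective 6. Section 8.1 also does not say which binary outcome is meant.

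The ceiling follows from the definitions alone. The contrast of 10.3% with 50% rests on assumed counts (6 operated, 3 pCR). With 4 to 10 operated and half of them pCR, the literal rate runs from 6.9% to 17.2% against the same 50%.

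The primary analysis, the two-stage rule, the sample size and the toxicity stopping rule are not affected. The finding does not extend to the averaging rule for multiple tumours, and it does not show that the reported percentage would be distorted.

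**What to change.** In 8.1:

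1. Replace the undefined rate with the pCR rate as defined in 7.3.2, reported with an exact binomial 95% interval.
2. State that its denominator is operated patients with an assessable specimen, as an exception to the TACE-completer population, and report how many operated patients had no assessable specimen.
3. Summarise percentage necrosis descriptively in the same patients, for example by median and range.
4. If a rate over all TACE completers is wanted, give it only as a supplement, labelled as combining resection with pCR.

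The averaging rule in 7.3.2 needs no change. The cost is a few lines of wording, with no new data and no effect on sample size. It should be settled before any pathology results are analysed, so that neither the outcome nor the denominator is chosen after the fact.
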